5.2 Assumptions of the Treatment Effect

Assumption for DFS

An average HR of 0.72 is assumed for DFS between nivolumab and placebo in CA209577 at the final DFS analysis, which accounts for the piece-wise HRs summarized in Table 5.1-1. This translates to a median DFS of 31 months in the nivolumab arm.

In many trials studying immunotherapies, the PFS and OS curves in the immunotherapy-treated arms tend to have a delayed separation from the control arms across tumor indications;¹⁰ therefore, the treatment effect for DFS is assumed to have a delayed separation with an HR of 1 for the first 3 months and a larger treatment effect after delayed separation with an HR of 0.667. After 5 years, the treatment effect for DFS is assumed to decrease slightly with an HR of 0.8. This takes into consideration that patients who have not had disease recurrence within 5 years of surgery are generally cured from the disease and the treatment effect is more reflective of the survival benefit.

Assumption for OS

The average HR of 0.73 is assumed for OS between nivolumab and placebo in CA209577 at the final OS analysis, which accounts for the piece-wise HRs summarized in Table 5.1-2. This translates to median OS of 44 months in the nivolumab arm.

The assumption of the OS treatment effect between the 2 arms follows the same thought process as the assumption of the DFS treatment effect. The treatment effect for OS is assumed to have a delayed separation with HR of 1 for the first 4 months, and a larger treatment effect after delayed separation with an HR of 0.685. After 6 years, the treatment effect for OS is assumed to decrease slightly with an HR of 0.8. This takes into consideration the combined effect of potential for more subsequent immunotherapies in the control arm and other effective subsequent therapies in both arms for long-term survivors.

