5.3 Sample Size and Power

According to the assumptions for DFS described in Sections 5.1 and 5.2, the study will require approximately 760 subjects to be randomized at a 2:1 ratio to nivolumab and placebo and observations of at least 440 DFS events in order to achieve approximately 91% power to detect an average HR of 0.72 at a 2-sided alpha of 0.05.

The sample-size determination accounts for 1 DFS interim analysis. Details of the DFS analysis timing are provided in Section 5.4.

It is estimated that these 760 subjects will be accrued and randomized within approximately 36 months from the first-patient first-visit (FPFV).

Overall survival will be tested following the overall hierarchical testing procedure¹¹ upon demonstration of superiority in DFS at either interim or final analyses for all randomized subjects.

With the sample size of 760, it is required to observe at least 460 OS events at the final OS analysis in order to achieve approximately 90% power to detect an average HR of 0.73 at a 2-sided alpha of 0.05. The power of the OS final analysis accounts for 2 OS interim analyses that occur at the same time as the DFS interim and DFS final analyses, respectively. Details of the OS analysis timing are provided in Section 5.4.

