- The key analyses of the primary endpoint DFS are the log-rank test and the Cox proportional hazards regression model, which are most efficient under the proportional hazard assumption. However delayed effect of immunotherapy interventions has been observed in many studies. The proportional hazards assumption will be examined by fitting a Cox model including a time-dependent variable defined by treatment by time interaction.

If the two-sided Wald Chi-square p-value of the treatment by time interaction is less than 0.1 or a visual examination of the K-M plot of the DFS indicates a delayed separation of the curves, the following analyses will be conducted in order to report the treatment effect when taking into consideration of the delayed effect.

– DFS will be compared between treatment groups via a 2-sided max-combo test. The max-combo test statistic is the maximum of 4 different Fleming-Harrington family weighted log-rank test statistics. $Z_m = \max (FH (0, 0), FH (0,1), FH (1,0), F(1,1))$, where $FH(p,\gamma)$ are the test statistics from the Fleming-Harrington family of test statistics. $FH (0, 0)$ corresponds to the log-rank test, while $FH (0, 1)$ is more sensitive to late-difference alternatives, $FH(1,0)$ is more sensitive to early difference with decreasing treatment effect and $FH(1,1)$ uses weights at the median.

– The DFS hazard ratios will be estimated in 2 time periods. The periods will be defined by a cutoff point. The cutoff point will be calculated in two ways: 1) using a stratified time-dependent Cox model with effects for treatment and period-by-treatment interaction. The cutoff point will be estimated using a grid of possible cut off points and obtained by maximizing the partial log likelihood. Ties will be handled using the exact method. A two-sided 95% CI for the hazard ratio will also be presented. 2) use the pre-specified cutoff point for delay separation used in the sample size determination, ie.3 months.

Visual interpretation of the curves may lead to additional analyses post database lock with more cut off points.

Sensitivity analyses for DFS to investigate alternative censoring schemes

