7.5.3.2 Sensitivity Analyses

- The sensitivity analysis specified in [section 7.5.2.1](#) will also be performed for OS when applicable. The sensitivity analyses specific for DFS will not be performed for OS.

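### The delayed-effect analyses of DFS run only after a weak interaction test or an undefined visual check, although the design itself assumes the delay

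*SAP*

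**What the plan says.** SAP 5.2 states the design assumption: "the treatment effect for DFS is assumed to have a delayed separation with an HR of 1 for the first 3 months". After that the DFS hazard ratio is 0.667, easing to 0.8 beyond 5 years. For OS it is 1 for 4 months, then 0.685, then 0.8 beyond 6 years.

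SAP 7.5.2.1 notes that delayed effects are common with immunotherapy. It examines proportional hazards by "fitting a Cox model including a time-dependent variable defined by treatment by time interaction", without saying whether time enters linearly, as a logarithm or as a step. The trigger for further work is "If the two-sided Wald Chi-square p-value of the treatment by time interaction is less than 0.1 or a visual examination"; the visual half asks only that the DFS Kaplan-Meier curves appear to separate late. Only then are two analyses done: a max-combo test, and hazard ratios in two periods. The periods are split once at a cut-off found by grid search and once by the instruction to "use the pre-specified cutoff point for delay separation used in the sample size determination", which is 3 months. The section adds that visual interpretation may lead to further cut-offs after database lock.

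For OS, SAP 7.5.3.2 says the sensitivity analyses of 7.5.2.1 "will also be performed for OS when applicable", and then that those specific to DFS will not be done for OS.

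**The concern.** The analyses that estimate or test a delay directly sit behind a pre-test, although the delay is already the planning assumption and the 3-month split needs nothing from the data. Two things follow.

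First, the objective half of the trigger may have little power for the assumed pattern, which is a step at month 3 on curves that run to about 48 to 58 months. If so, the decision passes to the other half: a look at the curves by arm, with no criterion and no named reader, made once the result is known.

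Second, estimates reported only after a significant interaction are selected. They will tend to show more early disadvantage and more late benefit than is true. A reader could then see a hint of early harm that the selection helped to create.

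**Working it through.** **Inputs.** SAP 5.3: "approximately 760 subjects to be randomized at a 2:1 ratio to nivolumab and placebo", and "at least 440 DFS events in order to achieve approximately 91% power to detect an average HR of 0.72" (two-sided 0.05); 460 deaths for OS at an average hazard ratio of 0.73 and about 90% power; accrual of about 36 months. SAP 5.4: looks at 374 and 440 DFS events and at 299, 368 and 460 deaths. SAP Tables 5.1-1 and 5.1-2: control hazards per month of 0.035, 0.035, 0.03, 0.02, 0.003 with cuts at 3, 12, 30 and 60 months (DFS), and 0.026, 0.026, 0.0205, 0.018, 0.002 with cuts at 4, 12, 30 and 72 months (OS). Assumed here: uniform accrual, no dropout, unstratified models.

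**The plan's own figures.** The documents give no power for the interaction test, so the check starts from the log-rank power. Schoenfeld: power = Φ(√(d × 2/3 × 1/3) × |ln HR| − 1.96).
- DFS: √97.8 × 0.3285 − 1.96 = 1.29, giving 90.1%.
- OS: √102.2 × 0.3147 − 1.96 = 1.22, giving 88.9%.

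Simulating the piecewise hazards (6,000 trials) gives 81.0% and 92.0% cumulative for DFS (SAP: 81%, 91%) and 44.1%, 71.6%, 90.3% for OS (SAP: 45%, 70%, 90%). The simulation model therefore represents the design.

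**Interaction test.** In the same trials, fit a Cox model with treatment + treatment × f(t) and count two-sided Wald p < 0.1:

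| Scenario | Linear t | Log t | Step at the delay |
|---|---|---|---|
| DFS, 374 events | 21.6% | 32.8% | 44.4% |
| DFS, 440 events | 20.8% | 33.7% | 46.0% |
| OS, 299 deaths | 21.1% | 29.6% | 38.2% |
| OS, 368 deaths | 20.2% | 30.0% | 39.9% |
| OS, 460 deaths | 19.0% | 30.4% | 41.1% |
| Proportional hazards, HR 0.72, 374 events | 10.8% | 10.4% | 11.0% |
| Proportional hazards, HR 0.72, 440 events | 10.4% | 11.7% | 11.0% |

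The proportional-hazards rows use 2,500 trials. Repeat simulations, including variants with scan-dated recurrence or slower early accrual, stay within 18–22% (linear), 27–34% (log) and 37–47% (step), and within 9–12% under proportional hazards.

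**Hand check of the most favourable case (step at 3 months, 440 events).**
- Table 5.1-1 puts both arms at 90.0% at 3 months, so early events ≈ 0.10 × 760 = 76 and late events ≈ 440 − 76 = 364.
- Variance of the difference in log hazard ratios ≈ 1/(76 × 2/9) + 1/(364 × 2/9) = 0.0592 + 0.0124 = 0.0716, so SE ≈ 0.268.
- z = |ln 0.667| / 0.268 = 0.405 / 0.268 ≈ 1.51.
- Power ≈ Φ(1.51 − 1.645) ≈ 45%, in line with the simulated 46.0%.

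The limit is the 76 early events, so a better choice of f(t) cannot rescue the test.

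**Selection.** Over all simulated trials the median DFS hazard ratio in the first 3 months is about 1.00, and 0.67 afterwards. Given that the linear-time test fired, the medians are about 1.13 to 1.16 and 0.64 to 0.65. With the log or step form the early figure is about 1.20.

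**The case against.** The strongest reply is that the two triggers are joined by an or, so a non-significant Wald test blocks nothing. The assumed curves (90.0% in both arms at 3 months, 50.9% against 38.3% at 2.5 years) have the shape the visual check looks for. This stands. A reader might infer that the analyses would be omitted 80% of the time; that figure is the miss rate of one trigger in its linear form. The chance of omission cannot be computed.

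Nor does the SAP say that p of 0.1 or more establishes proportional hazards, tempting as that inference is; the section itself warns of delayed effects. It would also be wrong to say that only a single Cox hazard ratio is reported otherwise. Kaplan-Meier curves and rates at fixed times with confidence intervals are unconditional or depend only on follow-up (SAP 7.5.2, 7.5.3.1, 7.5.3.5), and the interaction model is always fitted.

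The selection effect is modest beside its uncertainty. With about 51 and 25 early events, SE ≈ √(1/51 + 1/25) = 0.244, so an early hazard ratio of 1.15 carries a 95% interval of roughly 0.71 to 1.85. The 1.13 to 1.16 also conditions on the Wald trigger alone, not on the combined rule.

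Conditional sensitivity analyses are a habit of this SAP (the 10% thresholds in 7.5.2.1). Those thresholds, however, concern data quality; this one depends on the treatment result.

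**Conclusion.** The point holds as a cheap improvement to supportive analyses. If the SAP's assumption is exactly right, the Wald trigger fires in about 20% of trials with linear time and in at most about 47% in any form tested, against about 10% when hazards are proportional. The pre-specified delayed-effect analyses then hinge on an undefined, post-result look at the curves. Where the Wald trigger does fire, the early DFS hazard ratio is pushed up from 1 to about 1.13 to 1.16 at the median.

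These figures rest on the SAP's hazards, uniform accrual, no dropout and an unstated function of time. They say nothing against the primary log-rank test, its alpha or its power; the stated power already includes the delay.

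It should not be taken as settled that the gate applies to OS. SAP 7.5.3.2 points both ways, and the gated text names only the DFS plot and 3 months, whereas the OS design delay is 4 months. The OS rule is unclear, and that is itself worth correcting.

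**What to change.** In SAP 7.5.2.1, delete the condition. State that the max-combo test and the two-period hazard ratios at the pre-specified 3-month cut-off will be produced at each formal DFS analysis, whatever the interaction p-value or the shape of the curves. Keep the treatment-by-time model as a descriptive estimate with its confidence interval, and name the function of time.

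In SAP 7.5.3.2, state that the same analyses apply to OS with the 4-month design delay as cut-off. Produce them whenever OS results by arm are released under SAP 2.3; at an interim where OS is not significant, they go to the DMC only.

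The protocol's rationale for Revised Protocol 04 says that the first planned interim is complete. A change made now should therefore be dated and described as such for DFS; for OS it can still be prospective if the final analysis has not been run.

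The cost is a few sentences and a few extra outputs from programs already planned, with no change to alpha, sample size or the primary test. The small downside is some supportive tables that add little if hazards prove proportional.

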5.4 Efficacy Assessments

Study evaluations will take place in accordance with the flow charts in [Section 5.1](#).

Baseline assessments of the chest and abdomen should be performed within 28 days prior to randomization utilizing CT or MRI. Subsequent assessments should include chest and abdomen and any clinically indicated sites. Subjects will be evaluated for disease recurrence every 12 weeks from the date of first treatment (+/- 7 days) for the first 12 months, then every 12 weeks (+/- 14 days) between months 12 and 24, and then according to local standards with a minimum of one scan every 6-12 months between years 3-5.

Disease assessment with contrast-enhanced computed tomography (CT) scans acquired on dedicated CT equipment is preferred for this study. Should a subject have contraindication for CT intravenous contrast, a non-contrast CT of the chest and a contrast-enhanced MRI of the abdomen, should be obtained. A contrast-enhanced MRI of the chest is also acceptable instead of a non-contrast CT of the chest. The same imaging method as was used at baseline.

Refer to CA209577 imaging Site Operations Manual and/or Image Acquisition Guidelines for more specific details.

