7.5.2 Primary Efficacy Endpoint

DFS will be compared between treatment arms using a two-sided log rank test, stratified by the three randomization stratification factors as recorded in IWRS.

The HR for DFS with its corresponding two-sided $100 \times (1 - \text{adjusted } \alpha)\%$ CI will be estimated via a stratified Cox model with treatment arm as the only covariate in the model. Adjustment on the CI will be based on the reallocated alpha level.

DFS for each treatment arm will be estimated and plotted using the KM product-limit method. Median survival time will be computed using the KM estimate and a 95% CI for the median will be computed based on a log-log transformation of the survivor function.

Source of DFS Event

The source of DFS event will be summarized by treatment group:

- Recurrence (local recurrence, regional recurrence, distant recurrence)
- Death

Status of Censored Subjects

The status of subjects who are censored in the DFS KM analysis will be tabulated for each randomized treatment group using the following categories:

- 1) Censored on randomization date
 - a) no baseline disease assessment
 - b) no on-study disease assessment and no death
 - c) no on-study disease assessment but death with prior subsequent therapy or second primary cancer
- 2) Censored on date of last evaluable disease assessment on-study
 - a) Received subsequent anti-cancer therapy
 - b) Second non-esophageal and non-GEJ primary cancer
 - c) Still on treatment
 - d) In follow-up
 - e) Off study
 - i) lost to follow-up
 - ii) subject withdrew consent
 - iii) other

DFS rates at fixed time points (e.g. 6 months, depending on the minimum follow-up) will be presented along with their associated 95% CIs. These estimates will be derived from the Kaplan-Meier estimate and corresponding CIs will be derived based on Greenwood formula for variance derivation and on log-log transformation applied on the survivor function.

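### The two-period DFS hazard ratios at a likelihood-searched cut-off carry a 95% CI that allows for neither the search nor the trigger, so an ordinary interval under-covers

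*SAP*

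**What the plan says.** SAP 7.5.2.1 checks proportional hazards for DFS with a treatment-by-time term in a Cox model. The delayed-effect analyses are run only if the "p-value of the treatment by time interaction is less than 0.1 or a visual examination of the K-M plot" points to late separation. The time scale of the interaction (linear, log or other) is not given, and the visual criterion is not defined.

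One of those analyses estimates DFS hazard ratios in two periods from a stratified time-dependent Cox model. The boundary between the periods is set in two ways:

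- **Searched.** "The cutoff point will be estimated using a grid of possible cut off points and obtained by maximizing the partial log likelihood". Neither the range nor the step of the grid is stated. The text adds: "A two-sided 95% CI for the hazard ratio will also be presented". It names no CI method, makes no adjustment, and does not say that the interval is conditional on the chosen cut-off.
- **Fixed.** "use the pre-specified cutoff point for delay separation used in the sample size determination, ie.3 months". This matches SAP 5.2, where "the treatment effect for DFS is assumed to have a delayed separation with an HR of 1 for the first 3 months". It stands behind the same trigger, and the CI sentence is placed under the searched method.

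Further cut-offs may be added after database lock on visual grounds. SAP 7.5.3.2 carries the sensitivity analyses of 7.5.2.1 over to OS where they apply.

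**The concern.** Choosing the cut-off that maximises the partial likelihood favours the split at which the two period hazard ratios look most different in the data at hand. A CI computed as if that split had been fixed in advance is centred on an exaggerated contrast and is too narrow. The trigger adds a second selection, because the analysis appears mainly in trials where the early and late effects already look different.

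A reader of such output may see early harm and a strong late benefit, each with an interval labelled 95% that does not cover at that rate. No confirmatory decision depends on it. What is at stake is the description of how the treatment effect changes over time, which the design itself expects to be delayed.

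**Working it through.** **1. The plan's own figure.** SAP 5.3 states about 91% power with 440 DFS events, 2:1 allocation, hazard ratio 0.72 and two-sided alpha 0.05. Schoenfeld's formula is power = Φ(|ln HR| × √(d × p(1−p)) − 1.96). With |ln 0.72| = 0.3285 and √(440 × 2/3 × 1/3) = 9.89, this is Φ(3.248 − 1.960) = Φ(1.288) = 90.1%. With one Lan-DeMets O'Brien-Fleming interim at 374 events, cumulative power is 89.5%. Interim power is 79.6% (stated 81%) and the interim nominal level is 0.0301 (stated 0.03). The design inputs are therefore read correctly. The SAP gives no coverage figure to reproduce.

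**2. Simulation inputs.**
- From the SAP (5.1 to 5.3): 760 subjects at 2:1; control hazards per month of 0.035 to 1 year, 0.03 to 2.5 years, 0.02 to 5 years and 0.003 after; hazard ratio 1 to month 3, 0.667 to month 60, then 0.8; 36-month accrual; 440 events.
- Assumed: uniform accrual, no dropout, unstratified model, ordinary Wald CIs, and five grids (monthly over months 1–6, 1–12, 1–24 and 1–36; every 3 months over 3–24).
- Scan dating follows Protocol 5.4: "Subjects will be evaluated for disease recurrence every 12 weeks from the date of first treatment (+/- 7 days) for the first 12 months", then ±14 days to month 24, then "a minimum of one scan every 6-12 months between years 3-5". The main setting has scans every 8 months after month 24 and 10% of events at exact dates. Alternatives are 12-monthly scans with 5%, and 6-monthly scans with 30%. Event-free subjects are censored at the last scan (SAP 4.1.1).

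**3. Method.** The model is h(t) = h0(t) × exp{β1·x·1(t ≤ c) + β2·x·1(t > c)}. The chosen c maximises the partial log likelihood over the grid. Each interval is exp(β̂ ± 1.96 × SE). The target is the large-sample Cox hazard ratio of each period at the chosen c, under the same dating.

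**4. Coverage of the nominal 95% CI (early / late period, %).**

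| Grid (months) | Continuous, all trials (4,000) | Scan-dated, all trials (6,000) | Scan-dated, p < 0.1 linear time (1,132) | Scan-dated, p < 0.1 log time (1,778) |
|---|---|---|---|---|
| 1–6 | 89.7 / 93.6 | 93.0 / 94.1 | 86.0 / 91.9 | 87.0 / 91.7 |
| 1–12 | 87.9 / 91.5 | 90.8 / 92.4 | 79.4 / 87.2 | 82.5 / 88.6 |
| 1–24 | 87.3 / 87.2 | 89.3 / 88.3 | 75.4 / 75.8 | 79.9 / 82.4 |
| 1–36 | 87.3 / 83.2 | 89.0 / 85.1 | 75.6 / 69.9 | 79.8 / 79.5 |
| 3–24 by 3 | 90.6 / 88.8 | 90.2 / 89.2 | 78.2 / 78.7 | 81.8 / 84.4 |

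The p < 0.1 condition is met in 1,132/6,000 = 19% of trials on linear time and 1,778/6,000 = 30% on log time. Over the three scan settings the ranges are 82–94% (all trials), 66–92% (linear) and 77–92% (log). At the 374-event interim, in the main scan setting, they are 83–94% (all) and 65–92% (linear). Monte Carlo error is about 0.5 points for all trials and 1–2 points for triggered trials.

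**5. Separate simulation with other grids** (4,000 trials, continuous times, 440 events, all trials, early / late). Under the SAP model: 88.3/92.3% (grid 2–12), 86.1/88.0% (1–24) and 84.4/81.1% (1–36 by half-month). With a constant hazard ratio of 0.72, grid 1–24 gives 80.3/84.0%, and both intervals are right together in 66% of trials.

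**6. Full trigger.** The visual criterion cannot be simulated as written. Two assumed visual rules, each combined with linear p < 0.1, fire in 43–65% of trials and give coverage of 79–96%. The p-value-only columns are therefore the less favourable case.

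**7. Exaggeration** (grid 1–24, scan-dated, linear p < 0.1). Geometric-mean hazard ratios are 1.07 early and 0.58 late, against true values of 0.84 and 0.67. The early-to-late ratio is 1.07/0.58 = 1.84, against 0.84/0.67 = 1.25. On the same grid the searched cut-off lands within 2–4 months in only 34% of all trials and 23% of p < 0.1 trials, although the simulated change is at month 3.

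**8. Fixed 3-month split.** Coverage over the three scan settings is 94.6–95.4% in all trials and 91.8–93.8% in linear p < 0.1 trials. When the hazard ratio is in truth constant (0.72 or 1), the trigger alone lowers its coverage to 74–89% early and 91–96% late.

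**9. Repair by a simultaneous critical value.** Replace 1.96 by the critical value for the maximum over the grid (standardised Brownian motion at the grid's information fractions). This is 2.45–2.70 early and 2.21–2.71 late. Coverage over all scan-dated trials becomes 96.3–98.1%.

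**The case against.** This is a conditional sensitivity analysis, and significance rests on the stratified log-rank test. The SAP gives these hazard ratios a plain 95% CI. Several other sensitivity analyses get an interval at the primary significance level with a p-value, so this one can be read as descriptive. The fixed split is reported beside it. SAP 7.5.2 states that "DFS for each treatment arm will be estimated and plotted using the KM product-limit method", and 7.5.3.5 adds DFS rates at fixed times, so a delay can be seen without any search. The size depends on an unstated grid and CI method, and a search out to 36 months is unlikely when the assumed delay is 3 months. The most striking figures belong to the p < 0.1 subset, not to the full trigger. Before the trigger, late-period bias is small: in a continuous-time run the late hazard ratio is 0.64 against 0.67 for grid 1–24, and 0.66 against 0.68 for grid 1–6.

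Most of this stands as a limit on weight. It does not remove the point. The same section labels the p-values of its backward-selected model as descriptive, and 7.5.2 adjusts the primary CI for alpha, but the searched-cut-off interval gets neither. Even the shortest grid falls below 95% over all trials. In the same all-trials run with grid 1–24, the early hazard ratio is 1.04 against 0.88, so the exaggeration does not come from the trigger alone. The fixed split, which is the safeguard, sits behind that trigger too.

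**Conclusion.** The point holds. The SAP presents a 95% CI at a cut-off chosen from the same data, after a data-dependent trigger, and allows for neither. If the CI is an ordinary one, coverage over all trials is 82–94% under the SAP's delayed-effect model. It is lower in trials meeting p < 0.1, and unknown under the full trigger because the visual criterion is undefined. These figures rest on assumed grids, Wald intervals and an unstratified model; stratification should not remove the effect. OS was not simulated. The primary DFS test, the primary hazard ratio and type I error are untouched. The change should be made, but nothing confirmatory turns on it.

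**What to change.** 1. Report the period-specific DFS hazard ratios with 95% CIs at the pre-specified 3-month cut-off in every case, whether or not the trigger fires.
2. State the grid (range and step) and the time scale of the treatment-by-time interaction.
3. Present the searched cut-off and its hazard ratios as descriptive, without a nominal 95% CI. Alternatively, give an interval with a critical value simultaneous over the grid, computed regardless of the trigger; this is slightly conservative.
4. Use the same wording if the analysis is carried over to OS.

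The cost is SAP wording, or a short program for the simultaneous critical value. No data collection, design or alpha allocation changes.
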